### New Developments:

The in-office HIRREM approach used for research since 2011 remains very operator dependent (extensive Technologist education and experience required), and requires a lot of time for sessions (typically 10-20 sessions of 90-120 minutes each). To reduce the length of sessions, and reduce operator dependence, while increasing scalability, a new generation of hardware and software has been developed. Although based on the same core technology and algorithms for rapidly mirroring brainwaves back as audible tones in a closed-loop paradigm, the improved device includes the use of faster, 64-bit processing architecture for faster feedback, the use of 4 sensors, and the use of a standard series of protocols, all done with eyes closed (HIRREM-SOP). Although only 2 sensors are active at one time, the Technologist can apply 4 sensors at the same time. The software can switch from one pair to the other automatically, which effectively cuts in half the number of sensor placement changes needed during a session, yielding a shorter session time with fewer interruptions.

Informed by experience with prior controlled trials, the placebo condition has also been modified. The modified approach includes intentional randomness to both the pitch of the tones, as well as the timing and occurrence of the tones. In addition, characteristics of the tones themselves are not acoustically engineered. This appears to hold great promise as an improved placebo condition for use as a control in research evaluating this intervention.

This pilot study will evaluate feasibility of using this standardized, enhanced approach with HIRREM-SOP, and the effectiveness of the blinding for the placebo condition, in participants with symptoms of insomnia.

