There will be pre- and post-intervention data collection to include physiological outcomes (BP, HR, and measures of autonomic cardiovascular regulation), as well as symptom inventories for insomnia (Insomnia Severity Index, ISI, Pittsburgh Sleep Quality Index (PSQI), and the Epworth Sleepiness Score (ESS), depression (Center for Epidemiological Studies- Depression Scale, CES-D), anxiety (Generalized Anxiety Disorder-7, GAD-7), and stress (Perceived Stress Scale, PSS).

Measures will be collected at an enrollment visit (V1), and the intervention will begin 0-14 days thereafter. Post-intervention data collections will be obtained at 0-14 days (V2) following completion of the intervention, and 4-6 weeks (V3, primary outcome) following V2. Analyses for primary outcomes will include differential change in ISI from V1 to V3, and the expectation measure for group assignment prior to the 5th session. The blind will be broken at the V3 visit, and those in the NCC group will be offered the opportunity to cross over to receive acoustic stimulation linked to brainwaves. All study personnel except for the Technologists will remain blinded to group assignment, so that data collection will be carried out by individuals without knowledge of group assignment.

Sample Size and Statistical Analysis:

As a pilot study evaluating upgraded technology, and a standardized protocol, there are no data on which to base formal sample size estimates. The protocol is thus written with the goal of having 20 subjects (10 per group) to be enrolled and complete the study. For analysis, we will utilize linear mixed models (LMMs) to contrast longitudinal changes in ISI scores between the BCC and NCC groups. Mean contrasts will be used to compare the changes in ISI between groups from V1 to V3, our primary test of efficacy. Comparisons of changes in all secondary outcomes will be assessed in a similar fashion.

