#### Exclusion Criteria:

- Unable, unwilling, or incompetent to provide informed consent.
- Physically unable to come to the study visits, or to sit in a chair for several hours.
- Known seizure disorder.
- Known obstructive sleep apnea.
- Diagnosed periodic limb movement disorder or known restless legs syndrome.
- Known urinary problem (i.e. benign prostatic hypertrophy) which is the likely cause of the sleep disturbance.
- Severe hearing impairment (because the subject will be using ear buds during HIRREM-SOP).

- Ongoing need for treatment with opiate, benzodiazepine, or anti-psychotic medications, anti-depressant medications (SSRI, or SNRI's), sleep medications such as zolpidem or eszopiclone, stimulants such as Adderall, Provigil, or Ritalin, or thyroid hormone.
- Anticipated and ongoing use of recreational drugs, alcohol, or energy drinks.
- Weight is over the chair limit (285 pounds).
- Currently in another active intervention research study.
- Previous history of receiving or using HIRREM, Brainwave Optimization, HIRREM-SOP, or the wearable B2.

[figure not shown]
Participants are encouraged to discuss their participation with their health care provider following completion of the study because the intervention may alleviate some of the need for medications they were on previously. Participants are requested to abstain from using any alcohol or recreational drugs during the intervention, and until the final data collection visit for their group (V3 for BCC and V5 for those in the NCC group who decide to cross over) since use of these substances may cause reversal or cessation of any benefits. In addition, the participants are also advised to suspend chiropractic, cranial-sacral therapy, bio-energy work, and are asked to refrain from caffeine use after 1:00 pm during the intervention and until the one-month follow-up data collection.

Number of Sessions and Length of Study:

[figure not shown]

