In contrast, and toward the goal of evolving the paradigm for clinical trial methodology with respect to HIRREM-SOP, the present study is based on a maximally reductionistic hypothesis-testing and analysis strategy. In order to specifically identify the role of software algorithms – and to reduce not only provider-subject interactions but also limit the Technologist evaluation of brain activity patterns – as the basis for potential improvements, HIRREM-SOP sessions will be delivered based on a fixed set, and number of protocols (standard operating procedure) that will be identical for every client. The HIRREM-SOP protocols are designed based on cumulative experience of key personnel from the Wake Forest School of Medicine – Brain State Technologies academic-industry collaboration. These standardized protocols are projected to permit a robust majority of the benefits that have been reported to date, without introducing new or additional risk. Standardization of the HIRREM-SOP process will also reduce variability in the intervention delivery and thereby strengthen the generalizability of the study findings.

HIRREM-SOP sessions consist of only four potential paired placement options that are all run with eyes closed (F3/F4 and P3/P4, C3/C4 and O1/O2, FP1/FP2, and T3/T4, and AFZ/POZ and CB1/CB2). Each paired protocol will run two pairs of montages so that the participant is able to relax and have fewer disruptions during a session. In the past, the Technologists would change the placements between each protocol, so this will effectively cut in half the number of times the participant is interrupted while relaxing. While four sensors are placed on the participant's head at once, only two sensors are actively

mirroring. The other two sensors are simply observing how the brain is responding and recording that data. Each pair of protocol is set to play one at a time. For example, in the pair F3/F4 and P3/P4, F3/F4 will be mirrored back while P3/P4 are only observed. When the F3/F4 exercise concludes, the program will automatically start the P3/P4 mirroring protocol, while F3/F4 will be observed. At each location, based on the electrical pattern at the time, HIRREM-SOP software chooses what protocol will best support that area to relax itself. This process also provides information on how the brain is responding globally to shifts occurring locally.

Non-specific acoustic stimulation:

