Individuals assigned to the nonspecific acoustic stimulation group (NCC) will undergo sessions that mimic HIRREM-SOP in all appearances and procedures, including behaviors and subjective intentionality of the Technologist, and the number and scalp locations of protocols delivered during each session. However, in place of acoustic stimulation consisting of tones that vary in pitch and timing based on algorithmic analysis of real time brain activity, participants assigned to the NCC group will receive tones generated by a random signal generator. This includes randomness for both the timing, and the pitch of the tones, which are also not acoustically engineered. Technologists will be specifically instructed and trained to maintain comparable mental and behavioral interactional styles with all participants, both to minimize or eliminate confounding effects of Technologist subjectivity on differential outcomes associated with BCC and NCC groups, and to maintain subject blinding.

Safety:

Based on experience reported by Brain State Technologies, garnered from provision of case management support, feedback from their clients, and feedback from the HIRREM provider community, as well as results from IRB-approved studies at WFSM (now about 500 participants who have received HIRREM), the study team is not aware of any serious adverse events resulting from HIRREM sessions.

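### Do the unblinded Technologists, who run every session, call for a change to the trial's blinding?

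*Combined protocol and SAP*

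**What the plan says.** The Overview sets the blinding rule: "All study personnel except for the Technologists will remain blinded to group assignment". The reason it gives is that outcomes should be collected by people who do not know the arm. The Safety section has certified Technologists administer all sessions, and the Overview fixes these at 10 per participant, each lasting 1 to 1.5 hours.

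The HIRREM-SOP description that follows the flow chart gives the aim: "In order to specifically identify the role of software algorithms". It adds that "HIRREM-SOP sessions will be delivered based on a fixed set, and number of protocols (standard operating procedure) that will be identical for every client", and that at each scalp location "HIRREM-SOP software chooses what protocol will best support that area to relax itself".

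The section on non-specific acoustic stimulation makes the control (NCC) sessions look and run like the active (BCC) ones, "including behaviors and subjective intentionality of the Technologist, and the number and scalp locations of protocols delivered during each session". It also requires Technologists to be trained to interact with everyone in the same way, "both to minimize or eliminate confounding effects of Technologist subjectivity on differential outcomes associated with BCC and NCC groups, and to maintain subject blinding".

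Under Expectation Measure, participants say which arm they think they are in at V1, before session 5 and at V3. The guess before session 5 is the one of main interest. The Methods part of the Abstract labels the trial double-blinded; the Overview labels it single blind.

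**The concern.** The only people who know the arm are those who sit with the participant and deliver the intervention. The primary outcome is the participant's own rating of insomnia, so any encouragement or doubt conveyed during sessions could reach it. Blinded data collectors cannot remove an influence that has already acted.

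The plan wants to credit the software. As described, the sessions are largely standardised and software-run, so on a first reading the Technologist has no need to know the arm. The one stated safeguard, training, depends on the conduct of the unblinded person, and no check of that conduct is described. New Developments also says "The in-office HIRREM approach used for research since 2011 remains very operator dependent", which seems to make operator influence a live issue.

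At stake is the meaning of the effect estimate, which the Importance section intends for planning later trials.

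**Working it through.** The plan gives no figure for operator influence, so the check is mainly a comparison of the text, with one illustration of size.

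**1. Is it established that Technologists need not know the arm?** No.
- The sentence on software choosing the protocol describes active sessions.
- Control tones come from a random signal generator. Who selects that mode, and how, is not described.
- Ear buds appear under Exclusion Criteria as the reason for excluding severe hearing impairment. Nothing there says what the Technologist can hear, or what the operator screen shows.
- A coded arm setting would mean at most 24 settings, one per participant. Whether the software can run one, and at what cost, cannot be read from the documents.

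**2. Would masking the Technologists isolate the algorithm?** No. The Abstract, New Developments and the control description all say the control tones are also not acoustically engineered. The arm difference is therefore: link to brain activity + tone engineering + any operator effect. Masking removes only the third term.

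**3. How much exposure?** 10 × 1 h = 10 h to 10 × 1.5 h = 15 h per participant. This is session time, not time spent interacting. Protocols run with eyes closed, sensor pairs switch automatically, and placement changes are halved. No contact time is stated, so 10 to 15 h is an upper bound.

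**4. How large could the effect be?** Assumptions, none from the documents: SD of ISI change 4, 5 or 6; no true effect of the tones; operator effect b of 1, 2 or 3 ISI points; two-sided 5% t test. The plan supplies 10 completers per arm.
- Standard error = SD × √(2/10); noncentrality = b / standard error; df = 18; critical t = 2.101.
- Example, SD 5 and b = 2: standard error = 5 × 0.447 = 2.236; noncentrality = 2 / 2.236 = 0.894; rejection rate 13.6%.

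| SD | 95% CI half-width | b = 1 | b = 2 | b = 3 |
|---|---|---|---|---|
| 4 | 3.76 | 8.3% | 18.5% | 35.5% |
| 5 | 4.70 | 7.1% | 13.6% | 24.6% |
| 6 | 5.64 | 6.4% | 10.9% | 18.5% |

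Any such effect shifts the estimate one for one. Nothing in the documents indicates which value of b, if any, applies, or its sign.

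**5. Does the group guess settle the matter?** Not in either direction.
- The main guess follows 4 of the 10 sessions; the V3 guess follows all 10. A guess at V2 would follow the same 10 sessions as the V3 guess and would add little.
- If 10 of 20 guess correctly, the exact 95% interval is 27% to 73%. That limits the blinding outcome, but it does not measure operator conduct, because a guess can also reflect the tones or perceived benefit.

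**6. What would a conduct check involve?** Rating 10% of 24 × 10 = 240 sessions means 24 sessions, or 24 to 36 rater hours, with about 12 sessions per arm. It needs recording, consent wording, a blinded rater and a criterion for comparable behaviour. With about 12 sessions per arm, it could not show that conduct was the same.

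**7. Do the two labels mislead?** No. The Overview itself says who is unblinded, so anyone running or reporting the trial knows the arrangement whichever label is used.

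**The case for a change.** The case for a change is that the sponsor itself names Technologist subjectivity as a confounder and then relies on training that nobody verifies. The collected data cannot separate an operator effect from the effect of the tones, and pilot status is no defence when the estimates feed later trials. If the arm can be hidden, one coded setting per participant would be a small price. If it cannot, one sentence of explanation would help.

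Much of this stands. The contrast cannot be shown to isolate the algorithm, training is not verification, and the plan gives no reason for leaving Technologists unblinded.

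Two parts do not stand. The stronger claim, that the contrast fails because of operator behaviour, goes beyond the evidence, since no bias is shown. The remark on operator dependence concerns the education and experience needed for the legacy method, not knowledge of the arm. The coded setting is attractive only if the equipment already supports it, which the documents do not show. A sentence of explanation would inform readers but would leave the conduct of the trial, its data and its analysis as they are.

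**Conclusion.** No change is needed; this is a fair trade-off in a small pilot. The plan recognises the risk and applies the measures it can be seen to have: matched procedures, trained operators, blinded participants, blinded data collection, and a participant guess that includes one after the full course. None of the alternatives offers a demonstrated gain: masking is of unknown feasibility, session rating adds a new procedure with little power to reassure, and an extra guess nearly duplicates an existing one.

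The remaining limit is one of interpretation. A difference in ISI change should be read as the effect of the whole session package against this control, not of the algorithm alone. That would still be so with masked Technologists, because the tones also differ in engineering.

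The possible size is unknown. Under the assumed SDs of 4 to 6, an operator effect of 1 point would be small beside the pilot's own uncertainty, while one of 3 points would matter (false-positive rate 18.5% to 35.5%). The conflicting labels are a clerical slip that the Overview's own statement resolves. The conclusion would need another look if the existing software were known to hide the arm at no cost.

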**Importance:**

This study will explore the use of HIRREM-SOP for insomnia, in a randomized, controlled pilot clinical trial. Results will provide important insights regarding the effect of a new generation of this novel closed-loop, acoustic stimulation, applied using a standardized protocol and a fixed number of sessions. This, in a population shown to benefit from use of the legacy technology. It will confirm feasibility of use for the upgraded technology in this population, provide estimates of effect size, and assess effectiveness of blinding for a modified placebo control condition. All will be useful for planning future controlled trials. Although not anticipated with this small pilot trial, a positive result would suggest that HIRREM-SOP might have benefit as a noninvasive, non-drug alternative for initial management of sleep trouble. The study may also help to identify characteristics of subgroups that may experience differential effects/benefits from HIRREM-SOP.

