### Research Design and Method:

#### Objectives:

##### Primary Objective:

The primary objective of this randomized pilot study is to evaluate the effect of 10 sessions of standardized acoustic stimulation linked to brain activity (HIRREM-SOP, BCC), compared to 10 sessions of nonspecific acoustic stimulation not linked to brain activity (randomly generated, nonspecific tones, NCC), in addition to continued current care, on symptoms of insomnia, based on change in ISI score from V1 to V3.

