##### Tertiary/Exploratory Objectives:

Evaluate whether the addition of acoustic stimulation linked to brainwaves (BCC group), as compared to the addition of nonspecific acoustic stimulation not linked to brainwaves (NCC group), to continued current care, will result in greater differential changes in a variety of physiological, and behavioral outcome measures outlined below.

1. Autonomic nervous system functions, as manifested by heart rate, HRV, and BRS. We expect to see greater changes in autonomic activity and an improvement of sympatho-vagal balance in the BCC group. This would be reflected as changes in heart rate, and an increase of HRV and BRS parameters such as the standard deviation of the R-R interval (SDNN), rMSSD, HF alpha, and Sequence Up, Down, or All.
2. Additional behavioral outcomes such as insomnia (assessed by the Pittsburgh Sleep Quality Index, PSQI; and the Epworth Sleepiness Score, ESS), depression (as assessed by the Center for Epidemiological Studies-Depression Scale, CES-D), anxiety (as evaluated by the GAD-7), and stress (as assessed by the Perceived Stress Scale, PSS). We expect to see greater improvement in these symptom inventory scores in the BCC group.

Overview:

This will be a single site, single blind, placebo controlled, pilot clinical trial, enrolling adults who have insomnia. Assuming a potential dropout rate of 20%, up to 24 subjects will be enrolled to achieve a target of 20 subjects (10 per group) that complete the study. Subjects aged 18 or older, with symptoms of at least mild insomnia as defined by either subthreshold, moderate, or severe clinical insomnia by the Insomnia Severity Index (ISI  $\geq 8$ ), not attributable to another known cause (e.g. obstructive sleep apnea, restless legs syndrome, benign prostatic hypertrophy), will be randomly assigned to receive 10 sessions of acoustic stimulation linked to brain activity over 4 weeks (BCC), or 10 sessions of acoustic stimulation not linked to brain activity over 4 weeks (NCC). Sessions will be 1-1.5 hours in length. Both groups will continue their other usual care throughout.

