#### Participants/Subjects:

Adults ages 18 and older who have self-reported insomnia, who also meet inclusion criteria outlined below, and who are interested in receiving acoustic stimulation linked to brainwaves or acoustic stimulation not linked to brainwaves, will be considered for possible enrollment. Subjects will be recruited by physician referral, word of mouth, and through advertisement. The participant must be able to provide informed consent.

Interested subjects will be informed with a more detailed description of the study, and the extent of the time commitment will be explained through phone calls or email communications. If no exclusions are apparent from initial phone or email communications, potential participants will complete an online eligibility screening form, which will be reviewed by the study team.

As part of the informed consent process, study procedures, schedule for visits, and duration of participation will again be reviewed, and alternatives discussed, including the option to not enroll in this project, and follow up with their primary health care provider. For those confirmed to have an eligible baseline ISI score, baseline study measures obtained, and randomization will be completed prior to the start of the intervention. Those scheduled for an enrollment visit will also be provided a copy of Appendix B, Handout to Study Participants, and a welcome email with details.

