All baseline measures will be collected during the enrollment visit (V1), which will require 45-60 minutes. Zero to fourteen days after V1, participants will commence 10 sessions of acoustic stimulation linked to brain activity or not linked to brain activity, to be received over a one-month period. Since this is a fixed-dose intervention, every attempt will be made to complete all sessions within a two-week period. Sessions will be 1-1.5 hours in length. Participants will receive the first two sessions on consecutive days when beginning the intervention, and the first 3 sessions within the first five calendar days. To minimize participant time, following the first two sessions received as single sessions on consecutive days, up to two sessions might then be received per day, with a break of at least one hour between sessions.

Zero to fourteen days after the final intervention session there will be a post-intervention data collection visit (V2). All measures will be repeated. Four to six weeks after completion of the V2, there will be a post-intervention data collection visit (V3), with all measures repeated. Data collected at the V3 visit will comprise the primary outcome data for the study. The V2 and V3 visits are expected to require about 30 minutes. At V3, official study involvement is complete for those in the BCC group, while those randomized to the NCC group will be offered an opportunity to receive acoustic stimulation sessions linked to brainwave activity, to begin within one month of the V3 visit. Those who opt to do so will receive a course of acoustic stimulation linked to brainwaves, will continue to be followed for data collections at 0-14 days (V4) after crossover sessions, and 4-6 weeks (V5) after V4.

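### The primary ISI contrast has no stated adjustment for V1 ISI, so with 10 per arm its single estimate can carry part of a chance baseline difference

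*Combined protocol and SAP*

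**What the plan says.** The Primary Objective is "based on change in ISI score from V1 to V3". Under Sample Size and Statistical Analysis, "we will utilize linear mixed models (LMMs) to contrast longitudinal changes in ISI scores between the BCC and NCC groups", and then "Mean contrasts will be used to compare the changes in ISI between groups from V1 to V3, our primary test of efficacy". The Methods part of the abstract repeats the mean contrast for ISI but attaches the mixed model to systolic and diastolic blood pressure.

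No section names V1 ISI as a covariate, sets a common V1 mean across arms, or stratifies randomisation on ISI. The Overview admits participants with "symptoms of at least mild insomnia as defined by either subthreshold, moderate, or severe clinical insomnia by the Insomnia Severity Index" (8 or more on a 0–28 scale), so baseline severity can vary widely. On numbers it says: "Assuming a potential dropout rate of 20%, up to 24 subjects will be enrolled to achieve a target of 20 subjects", which is 10 per group. The Importance section says the pilot will "provide estimates of effect size" for planning later controlled trials.

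**The concern.** A contrast of change scores fixes the slope of V3 on V1 at 1. If the true slope is below 1, the arm that happens to start higher tends to show the larger fall without any treatment effect. Randomisation balances this over many hypothetical trials, but this trial yields one estimate, and with 10 per arm the V1 means can easily differ.

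Naming a mixed model does not settle the matter. The text fits a model with free V1 means, which does not adjust, and equally one with a common V1 mean, which does. The two can give different primary estimates from the same data. Because the estimate is meant to inform later trials, any chance V1 difference that it carries would pass into their assumptions.

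**Working it through.** **The plan's own figure.** 20 × 1.20 = 24 enrolled, as stated (20 / 0.80 would give 25). No power, alpha, SD or target effect is given, so there is nothing further to reproduce, and this point does not depend on the enrolment figure.

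**Inputs.** From the plan: n = 10 per arm; outcome V1-to-V3 change. Assumed, because the documents give no values: V1/V3 SDs (s1/s3) of 5/5, 4/5 and 4/6 points, and V1–V3 correlation ρ of 0.3, 0.5 and 0.7. A V1 SD below the V3 SD is plausible because entry requires ISI ≥ 8.

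**Step 1: does the mixed model adjust by itself?** In one simulated complete data set, the free-means model gave 6.354 and the raw change difference was 6.354. Constraining the V1 means to be equal gave 2.485, identical to the V1-adjusted V3 difference. This shows the algebra, not a typical gap: with the slope of 0.4 used there, it implies a V1 difference of −(6.354 − 2.485)/0.6 = −6.4 points, an extreme draw.

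**Step 2: chance V1 difference D.** SD(D) = s1 × √(2/10), which is 1.79 for s1 = 4 and 2.24 for s1 = 5. P(|D| ≥ 2) is 0.264 and 0.371.

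**Step 3: share carried.** With slope b = ρ × s3/s1, the change contrast given D has expectation (effect) − (1 − b) × D. For 4/5 at ρ = 0.5, b = 0.625 and the share is 37.5%, so D = 2 shifts the estimate by 0.75 points.

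**Step 4: precision.** Per-arm variance of change = s1² + s3² − 2ρ·s1·s3. Adjusted variance = s3²(1 − ρ²) × (1 + 1/(2n − 4)), with factor 17/16. Examples at ρ = 0.5:
- 4/5: 25 × 0.75 × 1.0625 = 19.92 against 16 + 25 − 20 = 21, ratio 0.949.
- 4/6: 36 × 0.75 × 1.0625 = 28.69 against 16 + 36 − 24 = 28, ratio 1.025.

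The change variance equals s3²(1 − ρ²) + s1²(1 − b)², so the ratio cannot exceed 17/16. It reaches that value when b = 1.

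| V1/V3 SD | ρ | Share carried | Shift per 2-point D | Variance ratio, adjusted/unadjusted | Trials with wider adjusted 95% CI | Variance ratio with dropout |
|---|---|---|---|---|---|---|
| 5/5 | 0.3 | 70% | 1.40 | 0.69 | 10% | 0.72 |
| 5/5 | 0.5 | 50% | 1.00 | 0.80 | 20% | 0.81 |
| 5/5 | 0.7 | 30% | 0.60 | 0.90 | 37% | 0.92 |
| 4/5 | 0.3 | 62.5% | 1.25 | 0.83 | 25% | 0.85 |
| 4/5 | 0.5 | 37.5% | 0.75 | 0.95 | 48% | 1.01 |
| 4/5 | 0.7 | 12.5% | 0.25 | 1.04 | 74% | 1.02 |
| 4/6 | 0.3 | 55% | 1.10 | 0.93 | 43% | 0.93 |
| 4/6 | 0.5 | 25% | 0.50 | 1.03 | 68% | 1.03 |
| 4/6 | 0.7 | −5% | −0.10 | 1.06 | 80% | 1.06 |

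**Step 5: simulation, complete data, 60,000 trials per cell.** At ρ = 0.5 the slope of the change contrast on D was −0.50, −0.37 and −0.26 (5/5, 4/5, 4/6). For the adjusted contrast it was within 0.01 of zero in all nine cells. The gap between the two estimates at ρ = 0.5 had medians of 0.7, 0.4 and 0.3 points and 95th percentiles of 2.5, 1.8 and 1.6. Approximate 95% half-widths, unadjusted and adjusted, were 4.70 and 4.21, 4.31 and 4.21, and 4.97 and 5.05.

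**Step 6: dropout.** The last column compares the common-V1-mean and free-V1-mean mixed models: 12 per arm, one lost before V2 and one before V3 in each arm, missing completely at random, V2 SD equal to V3 SD, V1–V2 correlation ρ, V2–V3 correlation 0.7, unstructured REML, 2,000 trials per cell, Monte Carlo error about 0.03. Normal-approximation 95% intervals from the common-mean model covered only 91% to 93%. That model and a complete-case V1-adjusted V3 difference disagreed with an SD of 0.24 to 0.58 points.

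**The case against.** The change contrast is a legitimate choice, used consistently for the outcome. It is unbiased over randomisations, and its simulated type I error is about 5%. The plan's wording does not exclude a common-V1-mean model, so adjustment is unstated rather than ruled out. All of that stands.

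The strongest point concerns the benefit. Averaged over randomisations, adjustment brings the estimate nearer the truth only through lower variance. The ratio exceeds 1 in three of the nine complete-data cells and four of the nine dropout cells. At ρ = 0.5 the V1 difference makes up 25%, 11% and 4% of the change contrast's variance (5/5, 4/5, 4/6), and the adjusted estimate was nearer the truth in 59%, 53% and 50% of trials. A shift of 0.5 to 1.0 points is also small beside a half-width of 4.3 to 5.0. So the gain may be close to nil if the V1 SD is well below the V3 SD.

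What remains is an asymmetry: the variance saving reaches 31%, while the complete-data loss is capped at 6.25%. The realised V1 difference will also be visible, and the unadjusted estimate then has an expected error that depends on it, which adjustment removes.

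Dropout is not a separate argument for adjustment, since a mixed model already uses partial follow-up; it bears only on the form of the model. Coverage with Kenward-Roger degrees of freedom was not simulated. Only the shortfall without a small-sample method was shown.

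**Conclusion.** The concern holds, as a recommended improvement and not as a claim that the test is invalid. The plan leaves open how V1 ISI enters its primary contrast, and one natural reading gives the raw change difference. With a V1 SD of 4 to 5, a V1 difference of 2 points or more arises in 26% to 37% of randomisations. At ρ = 0.5 the estimate then carries 25% to 50% of it; over all the assumed cells the range is −5% to 70%. Every size given here rests on assumed SDs and correlations, so confidence in the magnitude is medium. The absence of a stated adjustment, and the equality of the free-means contrast with the raw change difference under complete data, do not depend on those assumptions.

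**What to change.** Prespecify one model for the primary contrast: a linear mixed model of V1, V2 and V3 ISI with a common V1 mean across arms, group-by-visit effects at V2 and V3, unstructured covariance, REML, and Kenward-Roger degrees of freedom. The primary estimate is the BCC minus NCC difference in V1-to-V3 change from this model, so the outcome definition can stay as written. Participants with a missing V2 or V3 contribute the ISI values they have. Report raw mean changes by arm as descriptive, with the V1 and V3 SDs and their correlation, which later planning will need.

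As a separate drafting point, reconcile the abstract, which ties the mixed model to blood pressure, with Sample Size and Statistical Analysis, which ties it to ISI.

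The cost is two or three sentences and no new data, since ISI is already measured at V1. The statistical price is one degree of freedom and, with complete data, at most 1/16 (6.25%) more expected variance. If the V1 SD is narrower than the V3 SD, the adjusted interval may well be the wider one in a given trial (25% to 80% of trials in those assumed cells).
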